After selection of subject the researcher will sit for an interview with the subject. The researcher will at first introduce himself mentioning his institutional affiliation, conflict of interest and will supply address, contact telephone number and information about sponsorship. After that the subject will be thoroughly informed about the objectives and outcome of the study. Brief explanation of the procedure will be given to them. The subject will also be assured if any problem arises during the test; it will be taken care of. The result of the test will be sent to him free of charge and if any abnormality is detected, then appropriate management will be given to him, if possible or will be referred to specific treatment facility as appropriate. He will be encouraged for voluntary participation in a cordial and friendly attitude and will be allowed freedom to withdraw from the study whenever he likes even after participation. They will be informed about the method of confidentiality of their identification. Their identity will be recorded only in questionnaire which will be kept in safe custody with the researcher. It will not enter in the computer and will not go in any publication. No personal identification will be used in data analysis, report writing or publication. They will also be assured that interview time will minimum for maintaining their comfort, some questions will be asked about the personal, family and medical history without any private enquiry. The conflict of interest will be told to him if there is any. After he has understood these entire procedure, if he agrees to participate, then a willingly given informed written consent will be taken from him.

There is no possibility of any physical, social or mental risk of the respondent. A pretested questionnaire will be filled up by the research assistant.

All gathered information will be kept secret and only will be used for medical research and analysis.

SITE OF SAMPLE COLLECTION:

All the patients will be collected from the Out Patient Department (OPD) of National Institute of Diseases of Chest and Hospital (Annexure - I).

STUDY PROCEDURE:

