Investigator has applied for formal Clinical trials through www.Clinicaltrials.gov and was granted permission to go on with the trial (Annexure II) .On the first day of enrollment, the objectives, nature, purpose and potential risk of all the procedures used for the study will be explained in detail to each subject, with a cordial attitude giving emphasis on the benefits he might obtain from this study. He will be encouraged for voluntary participation and will be allowed to withdraw himself from the study even after participation, whenever he felt uneasy. If he agreed to be enrolled in the study, an informed written consent will be taken in a prescribed form (Annexure - IV). Detailed family history, medical history and thorough physical examination of each patient will be done and all the information will be recorded in a standard data sheet (Annexure - V). Then all the patients will be requested to attend the Department of Physiology at 9 am (about 1 and 1/2 hours after his breakfast) on the day of biochemical and spirometric examination.

On the examination day, 5 ml of venous blood will be collected and taken to the Hematology laboratory as soon as possible for the estimation of serum 25-hydroxycholecalceferol, serum glucose 2 hours after breakfast and serum creatinine. After that his height and weight will be measured and the spirometric lung function test will be done by using a portable spirometer. After getting all the biochemical and spirometric reports the final selection will be done, according to the inclusion and exclusion criteria.

Subsequently, all the eligible patients will be randomly assigned to either 'Control' or 'Study' groups and will be thoroughly informed about the objectives and detailed study procedure, once again. Then the patients will be examined for the baseline value of all the study variables in Day 1.

Again after 90 days the study variables will be collected from same 46 patients.

CONFOUNDING VARIABLES:

- Age: >40 years (Heideri 2015)
- Socioeconomic condition: Middle class (Martineau et al 2015)
- Smoking status: (Janssens et al 2010)
 - Current smoker = with history of active smoking
 - Ex-smoker = with history of 0 – 8 quit year
 - Duration = for >30 pack years
- BMI: 25 – 29.9 kg/meter-sq (Janssens et al 2010)
COPD patients at moderate stage according to GOLD criteria with > 4 years duration (Rees et al 2013)
- Stable COPD patients (Mehrparver et al 2010)
- Vitamin D₃ deficient: 30 ng/ml (Vitamin D council 2017)

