All the above mentioned variables will be similar ,statistically non significant in both the groups to ensure the minimization of their effects.

VITAMIN ADMINISTRATION :

Collection:

Vitamin D3

Ingredient

- Cholecalciferol (40,000IU)
- Microcrystalline Cellulose (58.1 gm)
- Butylated Hydroxy Toluene (0.2mg)
- Magnesium Stearate (3mg)
 - Gelatin Capsule Shell (1mg)

Dose : 80,000 IU/wk

Route : Oral

Placebo : Courtesy of Beximco Pharmaceuticals Limited Bangladesh

Ingredient : • Microcrystalline Cellulose (303.8gm) • Butylated Hydroxy Toluene (0.2mg)

- Magnesium Stearate (3mg)
- Gelatin Capsule Shell (1mg)

STUDY VARIABLES:

(1) Spirometric variables

- FVC (L) : Forced Vital Capacity
- FEV₁ (L) : Forced Expiratory Volume in 1st second
- FEV₁/FVC Ratio (%) : Forced Expiratory Ratio
- PEF_R (L/min) : Peak Expiratory Flow Rate
- FEF₂₅₋₇₅ (L/S) : Forced Expiratory Flow in the middle of FVC

(2) Oxygenation variables

- Resting SpO₂ (%) : Resting Peripheral Capillary Oxygen saturation

(3) Exercise tolerance variables

- 6MWD (meter) : Six Minute Walk Distance
- Level of Dyspnea : Modified Borg Scale

(4) Hematological variables

- 25(OH)D (ng/ml) : 25-hydroxycholecalciferol
- PTH (pmol/l) : Parathyroid hormone
- Ca²⁺ (mg/ml) : Ionic calcium
- PO₄³⁻ (mg/ml) : Ionic phosphate
- AP (U/L) : Alkaline Phosphatase

Subsequently a standard therapeutic treatment (according to GOLD guideline) (Annexure - VI) will be prescribed to all the selected stable moderate COPD patients. In addition, the patients of

the 'Study group' will be prescribed for 80000 IU of oral vitamin D₃ per week for consecutive 90 days . Along with this, all the patients of both the groups will be advised to continue ad lib (according to their own choice) diet.

Proper education will be given about drug , method of taking medication and medication plan. Afterwards, a good rapport will be built up to take time to time follow up over telephone and visiting patient's place . Schedule appointment , hotline and follow up will be maintained properly. They will be requested to attend the Department of Physiology again on the 90th day, to have the assessment of all the above-mentioned study variables

Any patient, who failed to follow the study procedure exactly during study period, will be dropped and a new one will be included to fulfill the desired total sample number. That's why extended sample should be taken to fulfill the total sample number.

Collection of blood sample (Afroza 2015):

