The 6MWT will be performed at indoors, along a long, flat, straight, enclosed corridor with a hard surface that is seldom traveled. The walking course will be 30 meter in length which will be marked every 3 meter. The turnaround points will be marked with a cone. A starting line, which marked

the beginning and end of each 60 meter lap, will be marked on the floor using brightly colored tape.

The subject will be asked to walk at his own maximal pace along the corridor from the end, covering as much ground as he can, during the allotted time, without running. He will be also advised to take rest if he will be too exhausted to continue the test. Standard phrases at regular intervals (every 60 seconds) will be used, like: “you are doing well,” “keep up the good work”. At the same time he will be also informed about the past time and how much has left before the test was completed.

If any of the subjects developed chest pain, intolerable dyspnoea, leg cramps, staggering, diaphoresis or pale appearance the test will be immediately stopped and the subject will be dropped. Again, when any subject will complete the total study procedure (according to the exact study design), he will be congratulated for good effort.

STATISTICAL ANALYSIS:

The results will be expressed as mean with standard deviation (mean \pm SD).

The data will be statistically analyzed by a computer with SPSS (Version 16.0) using Chi-square test,(to know the qualitative difference between the observed and expected result).Spirometric variables, oxygenation variables, exercise tolerance variables and hematological variables will be found between two groups of patients. If the variables are normally distributed , statistical analysis will be done by parametric statistical test. But if it is not normally distributed then it will be transformed into natural logarithm and again into anti logarithm, to make it normally distributed, then parametric statistical test will be done. Independent sample ‘t’ test between two groups, paired Student’s ‘t’ test within two specific measurements of different durations of each group will be done.

In the interpretation of results, ≤ 0.05 level of probability (p) will be accepted as significant.

PUBLICATION POLICY

- ❖ Scientific article to be published in a scientific journal.
- ❖ Presentation in scientific seminar or conference orally or through poster presentation.
- ❖ Website dissemination through internet version of JBSP.

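### The no-risk statement contradicts the plan's own text, and the visible plan has no procedure to record adverse events or count individual high calcium values by arm

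*Combined protocol and SAP*

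**What the plan says.** Under Ethical Implications, straight after the account of consent, the plan states: "There is no possibility of any physical, social or mental risk of the respondent". Under Study Procedure it says that "the objectives, nature, purpose and potential risk of all the procedures used for the study will be explained in detail to each subject". The six-minute walk procedure says: "If any of the subjects developed chest pain, intolerable dyspnoea, leg cramps, staggering, diaphoresis or pale appearance the test will be immediately stopped", and adds that "the subject will be dropped".

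The Study Variables list has a haematological group: 25(OH)D, PTH, calcium, phosphate and alkaline phosphatase. Calcium is entered as "Ca²⁺ (mg/ml) : Ionic calcium". These variables are assessed at baseline and on day 90. Under Statistical Analysis, "The results will be expressed as mean with standard deviation", followed by independent t tests between groups and paired t tests within groups at p ≤ 0.05. No limit value and no count of abnormal results is mentioned.

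After the variable list, the plan says that a patient who does not follow the procedure exactly "will be dropped and a new one will be included to fulfill the desired total sample number".

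Two provisions bear on individual safety. Ethical Implications says that test results go to the patient and that abnormalities will be managed or referred. The text after the variable list provides for telephone contact, home visits and a hotline.

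**The concern.** A plan that declares risk impossible has no stated reason to look for harm, and the visible text plans no harm outcome. The same protocol adopts the GCP principle that foreseeable risks are weighed against benefit before a trial starts. That cannot be done if risk is taken to be nil.

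At stake is what the trial could report. Followed as written, it would present lung function and walking distance by arm without any adverse-event table. The relevant chemistry would appear only as group means, which are insensitive to a few patients with high values. If affected patients are also dropped, even the means may not include them.

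**Working it through.** **1. The three statements side by side.** Ethical Implications: no physical risk is possible. Study Procedure: the "potential risk of all the procedures used for the study will be explained in detail to each subject". Six-minute walk: six signs, chest pain among them, stop the test. The first statement cannot be true if the other two are needed.

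**2. Where harm could be recorded.** The methods, the Study Variables list, the Statistical Analysis section and the visible part of the data sheet contain no adverse-event definition, collection, table or analysis. The annexures and the first part of the data sheet are not visible, so this absence is claimed only for the text that can be read.

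**3. What a comparison of means can show.** The plan gives no safety figure, calcium SD or power calculation, so there is nothing of its own to reproduce. The following is an illustration.

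- From the plan: 23 patients per group and significance level 0.05.
- Assumed: a two-sided test (sidedness is not stated), normally distributed values with SD 1, k treated patients raised by 3 SD, everyone else unchanged.
- Shift in the treated mean = k × 3 / 23.
- Rejection rate from 20,000 simulated trials of the independent t test. A second column uses a 5 SD rise.

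| k of 23 | Mean shift, 3 SD rise | Flagged, 3 SD rise | Flagged, 5 SD rise |
|---|---|---|---|
| 1 | 3/23 = 0.130 SD | 5.1% | 4.5% |
| 2 | 6/23 = 0.261 SD | 7.9% | 8.9% |
| 3 | 9/23 = 0.391 SD | 13.1% | 17.5% |

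The chance rate is 5%. A larger rise helps little because an outlying value inflates the SD as well as the mean. A count of values above a limit would show each such patient.

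**4. What 23 treated patients can show even with full recording.** The chance of at least one event is 1 − (1 − p)^23. For assumed true rates of 1%, 2%, 5%, 10% and 20% this gives 21%, 37%, 69%, 91% and 99%. If no event is seen, the one-sided 95% upper limit is 1 − 0.05^(1/23) = 12.2%. This limit comes from the sample size, and the fix does not change it.

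**5. The two drop rules.** They are separate. One drops and replaces a patient who departs from the procedure; the other drops a patient whose walk test is stopped and, at that point, says nothing of replacement. Study Procedure places randomisation before the day 1 measurements, so either rule can act on a patient who already has an arm. A patient who stopped his capsules because he felt unwell would fit the first rule. No visible text keeps the data of dropped patients.

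**6. Units.** Calcium and phosphate are in mg/ml in Study Variables and mg/dl on the data sheet. Since 1 mg/ml = 100 mg/dl, the labels differ by a factor of 100. PTH is in pmol/l in one place and pg/ml in the other. Values entered consistently would leave the t tests unaffected, but no result can be set against a laboratory limit until the unit is settled.

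**The case against.** The strongest reply is that the plan does not leave patients unwatched. Calcium is on the data sheet, abnormal results lead to management or referral, and there is a hotline with telephone and home follow-up. Calcium, phosphate, PTH and alkaline phosphatase are also compared between arms. All of this stands. A reader might infer that harm from the supplement could not be seen, or that the trial would have no harm data at all. The documents support neither: a high day-90 value could be noticed and acted on. What they lack is systematic collection and a report by arm.

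Other tempting readings also fail:

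- That the plan records no adverse events anywhere. Part of the data sheet and the annexures cannot be seen.
- That patients who become unwell are dropped and replaced. No rule says so; the removal of affected patients is a possibility that the rules leave open.
- That the walk-test signs are evidence about the supplement. They concern the walk test, and matter here only because they contradict the no-risk sentence.
- That calcium is the only safety analyte. The plan designates none, and the data sheet also carries creatinine and SGPT.

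It is also fair to say that the size of the calcium rise is assumed. The planned paired test was not simulated; its sensitivity depends on within-patient correlation, which the plan does not give.

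**Conclusion.** The concern holds in a limited form. The no-risk sentence contradicts two other parts of the plan. The visible text states no procedure for recording or analysing adverse events by arm, and it analyses calcium only by means and t tests, so harms would not be systematically captured or reported.

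Under the assumptions above, one to three treated patients with a 3 SD rise would be flagged in about 5% to 13% of trials. The exact percentages are illustrative. That a mean comparison is weak for one to three abnormal patients also holds at a 5 SD rise. The effect of the drop rules cannot be quantified, because the plan gives no expected dropout or event rate. This is a worthwhile and inexpensive correction. It makes no comment on the dose and does not show that harm is expected.

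**What to change.** 1. Replace the no-risk sentence in Ethical Implications with the foreseeable risks, so that it agrees with Study Procedure and the walk-test section.
2. Record adverse events by arm for every randomised patient, including those later dropped, at the follow-up contacts already planned and at day 90.
3. Beside the means, report the number per arm with day-90 calcium above the laboratory's own upper limit, among those measured. Give the number randomised but not measured, with the reason. The limit is used for reporting only and sets no clinical rule.
4. Reconcile the units between Study Variables and the data sheet: calcium and phosphate (mg/ml against mg/dl) and PTH (pmol/l against pg/ml).

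The cost is a text correction, a little more data collection and one extra table. The calcium count uses samples already planned. It does not require recalling dropped patients, for whom the plan provides no day-90 sample. The current follow-up is only occasional, so event recording will be as complete as those contacts are. The fix does not make the trial large enough for uncommon harms: no events in 23 would still be compatible with a rate of up to about 12%.

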**Effect of Vitamin D3 on Lung Function and Exercise
Tolerance in D3 Deficient COPD Patients**

ClinicalTrials.gov ID: NCT03781895

Document Date: December 23, 2018

PROJECT SUMMARY

Background: Chronic Obstructive Pulmonary Disease (COPD) is a major cause of morbidity and mortality throughout the world which is a preventable as well as treatable disease. It has some important extra pulmonary effects which may contribute to the magnitude of the severity of this disease. Standard therapeutic treatment alone does not optimize its remedy. Vitamin D₃ has been found to improve the physical efficiency of patients with various morbid disorders, including respiratory ailments. **Objectives:** To evaluate the effects of Vitamin D₃ on lung functions and exercise tolerance in patients with stable moderate COPD. **Methods:** For this, a prospective interventional randomized double blinded study will be carried out on 46 (eighty) vitamin D₃ deficient (serum 25 dihydroxycholecalciferol less than 30 ng/ml), male, stable (diagnosed patient, who has not experienced any acute exacerbation, hospitalizations, urgent care visits, or changes in routine medication within 4 weeks prior to study), moderate (post bronchodilator FEV₁/FVC < 0.70 of predicted value and FEV₁ = 50 to 79% of predicted value) COPD patients (age ≥ 40 years), who will be selected from the Out Patient Department (OPD) of the National Institute of Diseases of Chest and Hospital (NIDCH) and will be grouped as A (control) and B (study) groups, respectively. All the patients will be again designated as A0, A90 (with placebo) and B0, B90 (with D₃) for before and after 90 days of follow up. All the participants will be matched in terms of duration of COPD, history of smoking, occupation and socioeconomic status. Along with the standard pharmacological treatment of COPD, the patients of the 'Study group' will be prescribed for 80000 IU of oral vitamin D₃ per week for consecutive 3 months. Along with this, all patients both the groups will be advised to continue ad lib (according to their own choice) diet. At the very 1st day of the study, the lung functions will be assessed by measuring Forced vital capacity (FVC), Forced expiratory volume in one second (FEV₁), Forced expiratory ratio (FEV₁/FVC%), Peak expiratory flow rate (PEFR) and Forced mid expiratory flow of FVC (FEF_{25-75%}), with a portable digital spirometer. In addition, exercise tolerance will be assessed by change in 6 Minute Walk Distance (6MWD) in 6 Minute Walk Test (6MWT). Changes in peripheral capillary oxygen saturation (SpO₂) by Pulse Oximeter and degree of dyspnoea by Modified Borg Scale (MBS) will also be measured both before and after 6MWT to evaluate their change in both the groups. All these variables will be measured again after 90 days standard pharmacological treatment of COPD with D₃ intervention (B group) and also without D₃ intervention (A group). For statistical analysis, Chi-square test, independent sample 't' test between two groups, paired

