Standard therapeutic treatment schedule has a limited role in improving the physical capacity in COPD patients (Singh et al 2003). Various supplementations and extra-therapeutic measures have been tried to improve the functional capacity of the COPD patients (Boo2012; Biswas et al 2013; Ismail et al 2015). Vitamin D₃ supplementation is one of them. The principal goals of adding vitamin D₃ in the treatment schedule of these patients are to reduce symptoms and exacerbations, to improve quality of life and to increase physical and emotional participation in everyday activities which may not be adequately addressed by standard pharmacological regime alone for COPD (GOLD 2015). Recently, a number of studies have shown an association between vitamin D deficiency and severity of COPD (Janssens et al 2010; Ferrari et al 2010). In addition in a prospective study, FEV₁ was measured in patients with severe and very severe COPD both before and after vitamin D₃ supplementation and significant improvement was found (Zendedel et al 2015). On the other hand, one recent study reported no significant improvement in FVC, FEV₁ and FEV₁/FVC% in Vitamin D₃ deficient COPD patients after vitamin D₃ administration as compared to that of the control group (Jabbari et al 2013).

However the volume of information regarding the effect of vitamin D₃ administration in COPD patients is not enough for reaching any final conclusion. Moreover, with the best of our knowledge no study have been conducted to observe the effects of this fat soluble vitamin on the spirometric lung function status, oxygen saturation and exercise tolerance in vitamin D₃ insufficient, stable patients with moderate COPD.

Therefore, on the basis of this background the present study has been designed to evaluate the effects of Vitamin D₃ on the spirometric lung function status, peripheral capillary oxygen saturation and exercise tolerance in D₃ deficient, male patients with stable moderate COPD. This study will draw attention of the physicians about the beneficial effects of the vitamin D₃ on both pulmonary and extrapulmonary complications in COPD patients.

Research Question:

Does vitamin D₃ has any effect on lung function and exercise tolerance in Vitamin D₃ deficient stable COPD patients?

Hypothesis:

Null: Vitamin D₃ administration does not improve lung function and exercise tolerance in vitamin D₃ deficient stable COPD patients.

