Alternate: Vitamin D₃ administration improves lung function and exercise tolerance in vitamin D₃ deficient stable COPD patients.

Objectives:

General Objective

To evaluate the effects of vitamin D₃ administration on lung functions and exercise tolerance in vitamin D₃ deficient male patients with stable COPD.

Specific Objectives

[figure not shown]
- To measure the FVC, FEV₁, FEV₁/FVC%, PEF and FEF_{25-75%} of vitamin D₃ insufficient male patients with stable moderate COPD, in order to assess their lung function status.
- To measure the SpO₂ at rest, in order to assess the basal oxygenation status in this group of patients.
- To determine level of dyspnea at rest, in order to assess the basal breathlessness level in the same group of patients
- To measure the 6MWD of all the patients, in order to assess their functional exercise capacity.
- To measure both the SpO₂ and level of dyspnea again after 6MWT, for the assessment of their exercise tolerance.
- To measure all these variables after 90 days standard pharmacological treatment with vitamin D₃ and also without vitamin D₃ in stable COPD patients.
- To compare the results of baseline and endline.

Methodology:

Consolidated Standard of Reporting Trials:

(Moher et al 2010)

CONSORT 2010 Flow Diagram

TYPE OF STUDY : Prospective interventional randomized double blinded study

PLACE OF STUDY : Department of Physiology, Bangabandhu Sheikh Mujib Medical University (BSMMU), Shahbagh, Dhaka

STUDY PERIOD : March 2017 to February 2018

STUDY POPULATION : Stable, moderate COPD patients with vitamin D₃ deficiency.

SAMPLE SIZE : 46

SAMPLING : Simple random sampling .

GROUPING OF THE SUBJECTS :

Group A : 23 D₃ deficient COPD patients without D₃ administration
(Control group)

A0 : On day 0

A90 : On day 90

Group B : 23 D₃ deficient COPD patients with D₃ administration
(Study group)

B0 : On day 0

B90 : On day 90

Subject Selection:

Inclusion Criteria

- Age: >40 years (Heideri 2015)
- Socioeconomic condition: Middle class (Martineau et al 2015)
- Smoking status: (Janssens et al 2010)
 - Current smoker = with history of active smoking
 - Ex-smoker = with history of 0 – 8 quit year
 - Duration = for >30 pack years
- BMI: 25 – 29.9 kg/meter-sq (Janssens et al 2010)
- COPD patients at moderate stage according to GOLD criteria with > 4 years duration (Rees et al 2013)
- Stable COPD patients (Mehrparver et al 2010)
- Vitamin D₃ deficient: 30 ng/ml (Vitamin D Council 2017)

Exclusion Criteria

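### The instruction for the oral consent explanation stresses benefit, while the plan itself treats the effect as unknown, allocates half the men to control and elsewhere denies any risk

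*Combined protocol and SAP*

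**What the plan says.** **Study Procedure.** At enrolment, "the objectives, nature, purpose and potential risk of all the procedures used for the study will be explained in detail to each subject". The sentence goes on to say how this is to be done: "giving emphasis on the benefits he might obtain from this study". After random assignment, and before the baseline measurements, the men are briefed again on the objectives and procedure.

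**Ethical Implications.** This section describes the consent interview and states: "There is no possibility of any physical, social or mental risk of the respondent". It also promises every man free test results, and management or referral if an abnormality is found.

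**2. Rationale.** One before/after study in severe and very severe COPD found improved FEV₁. Against that, "one recent study reported no significant improvement in FVC", FEV₁ or FEV₁/FVC% relative to control in vitamin D₃ deficient COPD patients. The section concludes that the available information does not settle the question.

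**Methodology.** "SAMPLE SIZE : 46", with "Group A : 23 D₃ deficient COPD patients without D₃ administration" and the same number in group B. The Project Summary gives group A placebo, and the placebo's ingredients are listed under Vitamin Administration. The study is described as randomised and double blind.

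**Statistical Analysis.** Independent-sample t tests between groups and paired t tests within each group are planned, with significance at p ≤ 0.05.

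**The concern.** An explanation given before consent should reflect what is known. Here the plan says that the effect is uncertain, yet it directs staff to put the weight on benefit. This is an active instruction and not a gap in the text. A man who hears it could overestimate what he stands to gain, and his chance of receiving vitamin D₃ is one in two. The plan adopts freely given informed consent among its good clinical practice principles, and a one-sided oral explanation fits poorly with that.

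There is also a lesser statistical interest. The Introduction accepts that dyspnoea scales rest entirely on what the patient says. The six-minute walk is self-paced, and spirometry needs full cooperation and a forceful effort. Expectation could influence all three. SpO₂ and the blood variables are much less exposed.

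**Working it through.** The main check is a comparison of passages. A short calculation then shows which analysis expectation could reach.

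**1. What the sentence balances.** It names the risk of the procedures and the benefits of the study. Risk is to be explained and benefit is to be emphasised. Neither the supplement's risks nor the uncertainty of its effect is mentioned.

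**2. Whether other text restores the balance.** The Ethical Implications section denies any risk, which contradicts the potential risk mentioned in Study Procedure. The descriptions of the consent discussion in these two sections do not direct staff to mention placebo or uncertainty. The consent form might do so, but it was not available.

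**3. Share of men on control.** 23 + 23 = 46, which agrees with the stated sample size. The control share is 23 / 46 = 50%.

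**4. Between-group test.** Let the drug effect be δ and let expectation add e to the change in both arms. The mean change is e in group A and e + δ in group B, so the difference is (e + δ) − e = δ, and e cancels. The plan does not say whether the t test uses day-90 values or changes, but a shift common to both arms cancels either way. A simulation with δ = 0, 23 men per arm, a two-sided 5% level (the plan does not state sidedness) and 100,000 trials per setting gave:

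| Assumed shared shift e (SD of change) | Between-group test significant |
|---|---|
| 0 | 4.99% |
| 0.2 | 4.91% |
| 0.3 | 5.04% |
| 0.5 | 5.00% |

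The error rate stays at about 5%.

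**5. Within-arm paired tests.** With δ = 0 the expected change in either arm is e, so nothing cancels and the test is pushed towards significance whenever e is not zero. The documents give no value for e, nor for the part of it that comes from this phrase.

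**6. Timing.** Both briefings come before the baseline measurements. Expectation that is already present at baseline enters both readings and drops out of the change. Only the part that develops after baseline, such as a belief that the capsules have worked, contributes to e.

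**The case against.** The strongest reply is that the phrase should not be read apart from its sentence, which also requires the objectives, nature, purpose and procedural risks to be explained in detail. The benefits are conditional and undefined, and they could include the free tests and the management offered to every man. The consent form may say all that is needed about placebo and uncertainty. The denial of risk stands beside a sentence about the questionnaire and refers to a respondent, so it may have been meant only for the interview.

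Much of this stands. It is why the point is confined to the oral instruction and rated minor. It does not remove the asymmetry: the emphasis falls on benefit alone, and the risk clause does not reach the supplement. If the denial of risk is meant only for the interview, the text should say so.

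A reader might also infer from "This study will draw attention of the physicians about the beneficial effects" that patients are told the benefit is established. The documents do not support that. The sentence concerns physicians, and the Rationale goes on to pose a neutral research question and a null hypothesis. Nor does the cited null study bear on walk distance or Borg score, since it is cited for spirometry only.

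A reader might further infer that the emphasis would lead control men to take vitamin D themselves. Nothing in the text suggests this. Under the stated blind, control men would not know that they are controls, and 25(OH)D is among the variables reassessed on day 90.

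**Conclusion.** The oral consent instruction is one-sided by the plan's own account of the evidence, and it sits beside contradictory statements about risk. The severity is minor and the correction is worthwhile because it costs so little. No judgement is made on the consent form.

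The effect on outcomes is secondary and unquantified. Shared expectation does not bias the between-group comparison, provided that the stated double blind holds. It can add to the before/after change that the paired tests examine.

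A reader might be tempted to put a figure on this. An assumed shift of 0.3 SD of the change score would make a paired test with n = 23 significant in about 28% of trials with no drug effect (15% at 0.2 SD, 63% at 0.5 SD). These figures do not measure the harm from this phrase, for three reasons:

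- The shifts are assumed; nothing in the documents supplies them.
- The calculation places the whole shift in the change, although the men are briefed before baseline.
- It takes zero expectation as the comparison, whereas a neutrally worded placebo-controlled trial also raises some. Only the increment due to the wording would count.

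The figures show how paired tests respond to any change that is not due to the drug, including change from the standard treatment given to everyone or from repeating the tests.

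**What to change.** 1. In Study Procedure, replace the phrase about emphasis with: *explaining with equal weight that it is not known whether vitamin D₃ helps, that half the patients receive placebo, and the possible benefits and risks*.
2. Use one neutral script containing this wording, both at enrolment and at the briefing after assignment.
3. Reconcile the denial of any risk in Ethical Implications with the potential risk mentioned in Study Procedure. Without this, the new wording would still conflict with the plan.

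The cost is one sentence in each of the two sections and a short script. Recruitment may be slightly slower. Design, sample size and analysis are unchanged. The rewording does not protect the paired tests from other sources of before/after change.
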